1. INTRODUCTION

Atrial fibrillation (AF) is the most common arrhythmia and constitutes an important public health burden, being a source of high morbidity and mortality.¹ Circumferential pulmonary vein isolation (PVI) has become a mainstay in the treatment of AF, particularly in symptomatic patients with paroxysmal AF (PAF) intolerant or refractory to medical treatment.² Dormant conduction and pulmonary vein reconnections are responsible for AF/atrial tachycardia (AT) recurrences owing to incomplete non-transmural ablation lesions that generate gaps on ablation lines.³⁻⁵

Local electrogram attenuation, catheter-tip temperature and impedance drop have been used as surrogates for lesion formation. Nevertheless, they correlate badly with contact force and therefore constitute bad predictors of lesion size⁶. Radiofrequency (RF) power, duration of RF energy delivery, baseline impedance and contact force (CF) have been proven to be determinants of lesion formation.⁷⁻⁹

More complex formulae have been developed to assess real-time effect of RF delivery and predict threshold values that must be reached to reduce reconnections and achieve permanent PVI. Namely, Force-Time Integral (FTI) which is calculated in grams second (gs) and represents the area under the CF/time curve^{10,11}; and Ablation Index (AI) which is a complex weighed formula that integrates CF, RF time and RF power^{12,13}. In order to minimize PVI reconnection, FTI and AI threshold values have been studied. In general, these values must be higher in the roof and anterior wall as compared to the inferior and posterior wall probably related to a lower wall thickness.¹⁴

The CLOSE study¹⁵ analyzed the utility of AI for the reduction of AF recurrences with 91.3% of the patients free from AF/AT/atrial flutter (AFL) at 12 months follow-up. The CLOSE protocol targeted an inter-lesion distance of 6 mm and AI \geq 400 at the posterior wall and \geq 550 at the anterior wall. Nonetheless, in over 40% of patients, the target AI of 400 was not attained on the posterior wall owing to chest pain and/or intraesophageal temperature rise (IQR: 378–425 AU). The same 550 and 400 AI target values were used in a retrospective study comparing AI vs. CF-guided ablation resulting in significantly lower AT/AF recurrences on the AI arm.¹³ Such targets were chosen based on a previous study that retrospectively analyzed the ablation settings at first AF ablation of patients having redo ablation. Mean AI and mean FTI being statistically lower for reconnected segments [mean AI: 395 (350–429) vs. 422 (380–464), $p=0.002$; mean FTI: 311 (225–373) vs. 371 (260–502) gs, $p=0.003$].¹²

The left atrial wall is a thin structure with heterogeneous thickness, ranging from < 1mm to > 5 mm, with an important inter and intra-patient variability.¹⁶ This variability in wall thickness is the result of a complex array of three-dimensional muscular strands.¹⁷⁻¹⁹ A prospective study already showed that first pass PVI was limited by inability to create

transmural lesions in certain anatomical sites where left atrial wall thickness (LAWT) had been described as being higher in ex-vivo hearts.^{18,20} LAWT was an independent predictor of reconnection,²¹ dormant conduction²² and AF recurrence after 12 months follow-up,²³ and it might even be a predictor of transition from paroxysmal to chronic AF.²⁴

The relationship between FTI and AI values, LAWT and gap formation on the ablation line after PAF ablation was already studied in two small retrospective studies that used single-point LAWT measurements. Nevertheless, the anatomical location of the measured points in the multidetector cardiac tomography (MDCT) may have not corresponded exactly to the real-time catheter position as seen with the CARTO Merge® (Biosense Webster, Diamond Bar, CA, USA) module. These studies showed that FTI/wall thickness and AI/wall thickness indexes have demonstrated to predict gaps on PVI lines.²⁵ Although this relationship might also be explained by the fact that the anatomical regions where tissue is thickest are also regions where catheter stability is more difficult to obtain. Therefore, AI is the most suitable index to look at since it also takes stability on account.

Even though many limitations have been described on MDCT atrial wall thickness measurement for previous generations of scanners, modern machines allow for sub-millimetric resolution. In fact, MDCT-derived LAWT measurements have been reliably validated on a porcine model.²⁶ 3D LAWT maps have already been generated from contrast-enhanced MDCT images,²⁷ although their integration on a 3D anatomical mapping system for clinical use has not been described yet.

Of all the determinants of lesion creation, LAWT is one key element that has been evaluated in some retrospective analysis but is not yet used as per procedure to dose the radiofrequency delivery. Adapting AI to local LAWT would be very useful in standardizing the ablation procedure with parameters fitted to each patient, enabling the development of a personalized approach that will both: i) increase efficacy by performing transmural lesions to prevent the formation of conduction gaps in the initial lesion set, and ii) increase safety by preventing excessive RF delivery on thin wall areas which can lead to complications, like cardiac perforation or atrio-esophageal fistula.

Further on, with regards to procedural safety, a recent study by Pambrun et al.²⁸ recruited 100 patients with symptomatic, drug-refractory AF that underwent standard wide antral circumferential ablation to achieve PVI, divided into two groups: i) Control group, corresponding to 50 consecutive patients that followed a standard, two-catheter approach (CF ablation catheter plus circular mapping catheter); and ii) study group, conformed by 50 consecutive patients that followed a single-catheter approach (without the need for a circular mapping catheter) to achieve PVI. The rationale for the use of this approach was based on prior studies that showed that the complete loss of pace capture directly along the circumferential ablation line correlates with entrance block in 95% of PV and can be

achieved without circular mapping catheter guidance.^{29,30} Moreover, pacing for unexcitability along the ablation line can identify potential sites with dormant conduction, and even excitable sites that would not have been identified using adenosine,³¹ which, on the other hand, has not been able to improve the long-term success after AF ablation.³² The study by Pambrun et al.²⁸ showed that antral exit block validated with a CF-sensing ablation catheter successfully predicts PVI, and it was demonstrated that this single-catheter approach for achieving PVI is feasible, cost-saving and non-inferior in terms of AF recurrences in the mid-term. However, the study was conducted only in patients with PAF, normal LA volumes and no prior AF ablation procedures. Thus, the potential usefulness of this cost-saving approach in a broader, 'real life' population is still unknown. We hypothesize that a single-catheter approach for RF-based PVI may be feasible, cost-saving and at least as safe and effective as the standard approach when used in all patients referred for AF ablation.

Finally, one key element regarding procedural safety is the avoidance of a dreaded complication, the atrio-esophageal fistula.³³ It is estimated to occur in <0.1% to 0.25% of AF ablation procedures, but, among causes of death after AF ablation, atrio-esophageal fistula is the second most common along with stroke.³⁴ The relationship of the esophagus to the LA posterior wall and pulmonary veins is variable. It tends to be located farthest from the right superior pulmonary vein, but it can be close to any of the others, depending on its course, and may be within a few millimeters at the point of closest proximity.³⁵ Imaging of the esophagus may be performed as a component of an imaging study that is primarily designed to evaluate extraesophageal anatomy, such as during a cardiac MDCT. In a similar way as for LAWT measurements using MDCT, the distance (i.e. 'tissue thickness') between the posterior wall of the LA and the esophagus can be measured.

[figure not shown]
We sought to evaluate the feasibility, safety, efficacy and reproducibility of performing atrial fibrillation ablation procedures with a fully personalized protocol that includes: i) the use of MDCT-derived LAWT information to select tailored point-by-point AI targets; ii) the use of a single-catheter strategy to minimize vascular-related complications; and iii) the integration of a MDCT-derived 'fingerprinted' esophagus image to modify the ablation lines to avoid too close proximity of RF applications. The study will be single-catheter-based, hypothesizing that this simplified and personalized approach is feasible, cost-saving and at least as safe and effective as the standard approach when used in all patients referred for AF ablation.

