2. HYPOTHESIS AND OBJECTIVES

2.1 Research hypothesis

Personalized AF ablation using the ‘*ablation-by-LAW*’ protocol that uses point-by-point adapted AI values according to the local MDCT-derived LAW_T, is feasible, safe and at least as effective as the current AF ablation standards.

Ablation-by-LAW involves the use of tailored point-by-point AI values according to the local MDCT-derived LAW_T, the use of a single-catheter strategy, and the integration of a MDCT-derived ‘fingerprinted’ esophagus image to modify the ablation lines aiming to avoid too close RF applications, while performing the procedures using general anesthesia and a high-rate, low-volume ventilation protocol. The following diagram constitutes a general overview of the protocol:

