2.2.2 Secondary objectives

- To determine if the *ablation-by-LAW* approach permits to be more efficient in terms of procedure time, RF time, and fluoroscopy time.
- To evaluate the rate of complications using the *ablation-by-LAW* approach.
- To analyze the reasons for not obtaining a first-pass isolation using the *ablation-by-LAW* approach.

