3.11 Statistical analysis

3.11.1 Sample size

The sample size calculation has been based on the assumption that the proposed ablation protocol ('LAWT') is an acceptable alternative to the CLOSE protocol¹⁵ (non-inferiority), with the advantage of less radiofrequency applied and likely lower risk for complications. A non-inferiority margin of 10% of clinical success (arrhythmia-free survival one year after the ablation procedure) will be considered to be the largest difference that is acceptable

between both protocols for LAWT to be adopted in clinical practice. Recruiting $n = 106$ participants will be required to confer 90% power to reject the inferiority null hypothesis, that is, that the lower limit of a one-sided 95% confidence interval will be above the non-inferiority limit of -0.05 , indicating no difference between the arms. A drop-out rate of 10% is estimated, and included in the sample size calculation.

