3.13 Harms

Since all included patients must have an indication for AF ablation, no specific harms are expected in the context of the trial, as AI targets will be decreased at those ablation points with lower LAWT values. In fact, in a single-center, prospective series of 80 patients, whose results will be presented at the EHRA 2020 Congress, there were no procedure-related complications using this approach. All complications will be documented as secondary endpoints.

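### The hypothesis wording on safety goes beyond the descriptive safety objective, and complication rates are to be reported without confidence intervals in a single-arm study of 106 patients

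*Combined protocol and SAP*

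**What the plan says.** Safety appears in the combined protocol and SAP at three levels of strength.

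- **Comparative.** The introduction closes with the hypothesis that "this simplified and personalized approach is feasible, cost-saving and at least as safe and effective as the standard approach".
- **Absolute.** The formal hypothesis in section 2.1 is that the approach "is feasible, safe and at least as effective as the current AF ablation standards". Here the comparison belongs to effectiveness, and safety stands alone with no threshold.
- **Descriptive.** The objective in section 2.2.2 begins "To evaluate the rate of complications using the" and sets no reference value. Section 3.5.2.2 lists 14 complication types to be collected, also with no limit attached.

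The design in section 3.1 is single-arm. Section 3.11.1 sizes the study on arrhythmia-free survival only (n = 106, where these "participants will be required to confer 90% power to reject the inferiority null hypothesis"), with a 10% drop-out said to be included. It mentions a probable reduction in complications as an advantage of the approach. Section 3.11.2 summarises categorical variables as number and percentage and plans no interval for complications.

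The only background complication rate given is for atrio-esophageal fistula: "It is estimated to occur in <0.1% to 0.25% of AF ablation procedures". Section 3.13 adds that in a single-center series of 80 patients "there were no procedure-related complications using this approach", also without an interval.

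**The concern.** Effectiveness has a named comparator, a margin and a power statement. Safety has none of these, although the introduction puts the two side by side in one claim. In the text available (a few passages had been removed, and nothing is asserted about them) there is no reference complication rate, acceptable limit or interval against which the approach could be judged safe, or as safe as standard practice.

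What is at stake is how few or zero complications would look in the report. Under section 3.11.2 a complication that does not occur would appear as 0 (0%). Beside a hypothesis of safety, that figure looks stronger than it is. This matters most for fistula, the rare event that motivates the esophagus image and the one this study can say least about.

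**Working it through.** **Inputs**

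- Planned patients: 106 (section 3.11.1).
- About 95 evaluable: 106 × 0.90 = 95.4, from the 10% drop-out that section 3.11.1 says is included. Sections 3.4.3 and 3.10.3 also exclude cases after the procedure, but give no number and do not say whether this applies to complication reporting.
- Fistula rate: 0.1% and 0.25% (section 1). The values 0.5% (double the upper figure) and 1% are illustrations, not document figures.
- Earlier series: 0 complications in 80 patients (section 3.13).

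**The plan's own figure.** The 106 is an efficacy sample size; the plan gives no size, power or precision for safety. As a check, assume the CLOSE study's 91.3% from the introduction as the reference rate, with a 10% margin, one-sided 5% and 90% power. The single-arm formula gives

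n = [1.645 × √(0.813 × 0.187) + 1.282 × √(0.913 × 0.087)]² / 0.10² ≈ 101,

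and 101 / 0.9 gives 113 with drop-out. So 106 is not exactly reproduced. That is a separate efficacy matter; here 106 serves only as the planned number of patients.

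**Step 1: expected fistulas, n × p.** At 0.1%: 106 × 0.001 = 0.11. At 0.25%: 106 × 0.0025 = 0.27. At 0.5%: 106 × 0.005 = 0.53.

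**Step 2: chance of seeing none, (1 − p)ⁿ.**

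| True fistula risk | n = 106 | n = 95 |
|---|---|---|
| 0.1% | 0.999¹⁰⁶ = 89.9% | 90.9% |
| 0.25% | 0.9975¹⁰⁶ = 76.7% | 78.8% |
| 0.5% | 0.995¹⁰⁶ = 58.8% | 62.1% |
| 1% | 0.99¹⁰⁶ = 34.5% | 38.5% |

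**Step 3: exact upper limit when no event is seen.** One-sided 95%: 1 − 0.05^(1/n). Two-sided 95%: 1 − 0.025^(1/n).

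| Result | One-sided | Two-sided |
|---|---|---|
| 0/106 | 2.8% | 3.4% |
| 0/95 | 3.1% | 3.8% |
| 0/80 | 3.7% | 4.5% |

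For 0/106 the limits are 2.79 / 0.25 ≈ 11 and 3.42 / 0.25 ≈ 14 times the protocol's upper fistula figure.

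**Step 4: patients needed for a 95% chance of at least one fistula, ln(0.05) / ln(1 − p).** At 0.25%: 1,197. At 0.5%: 598.

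**The case against.** The strongest reply is that the plan already treats safety descriptively. Section 2.2.2 sets out to evaluate a rate, section 3.5.2.2 collects events, and section 3.13 calls them secondary endpoints. No safety test, margin or decision rule is planned. The comparative wording is confined to the introduction; section 2.1 says only that the approach is safe. All of this stands. It means the defect is a mismatch between the hypothesis wording and the objective, not a faulty analysis.

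A second reply is that fistula is only one of 14 listed complications and is too rare for any study of this size. That also stands: step 4 shows the limit is general and not a flaw particular to this plan. For the overall complication rate, 106 patients are more informative. But the documents give no overall reference rate, so a statement of comparative safety remains untestable here too.

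Three stronger readings are tempting and are not supported:

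- *That the study would almost certainly miss a doubled fistula risk.* At 0.5% the chance of no events is 59%, which leaves a 41% chance of at least one. Zero is the single most likely result, but far from certain.
- *That the investigators will present zero events as proof of safety.* No section says how zero events would be interpreted. Section 3.13 does cite the 80-patient series in support of expecting no specific harm, but its first reasons are that patients already have an indication and that energy targets are lowered where the wall is thin.
- *That the trial is too small and should be enlarged for safety.* It was not sized for safety and does not claim to be.

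**Conclusion.** The point holds as a minor one. Sections 1 and 2.1 say more about safety than a single-arm study with a descriptive objective can establish, and section 3.11.2 omits the intervals that would show a reader how little zero events prove. With 106 analysed, no fistulas would be compatible with a risk of up to about 3.4% (two-sided 95%), or 3.8% with about 95 analysed. The chance of seeing none is 77% at the protocol's upper figure and 59% at twice that.

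These results assume independent patients with a common risk, and complete ascertainment of fistula among those analysed. The 95 rests on the stated drop-out; further post-procedure exclusions, if applied to safety, would widen the limits. Nothing here suggests that the approach is unsafe, and the primary endpoint, its analysis and the sample size are unaffected.

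**What to change.** 1. **Sections 1 and 2.1:** remove the statements that the approach is safe, or at least as safe as standard, as conclusions the study can establish. Describe the safety aim in the terms already used in 2.2.2.
2. **Section 3.11.2:** report each complication listed in 3.5.2.2, and the proportion of patients with any of them, with exact 95% confidence intervals. Compute these on the number actually analysed, and state that number, rather than fixing 3.4% in advance. The any-complication figure mixes events of very different gravity (death and prolonged hospitalization, for example), so it should accompany the individual rates and not replace them.
3. **Section 3.11.2:** state that no conclusion on comparative safety or on fistula risk will be drawn.
4. **Section 3.13:** give the interval with the earlier series: 0/80, upper 95% limit 3.7% one-sided or 4.5% two-sided.

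The cost is some rewording, a few extra columns in the complications table and a more modest safety claim. No additional patients or visits are needed.

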2. HYPOTHESIS AND OBJECTIVES

2.1 Research hypothesis

Personalized AF ablation using the ‘*ablation-by-LAW*’ protocol that uses point-by-point adapted AI values according to the local MDCT-derived LAW_T, is feasible, safe and at least as effective as the current AF ablation standards.

Ablation-by-LAW involves the use of tailored point-by-point AI values according to the local MDCT-derived LAW_T, the use of a single-catheter strategy, and the integration of a MDCT-derived ‘fingerprinted’ esophagus image to modify the ablation lines aiming to avoid too close RF applications, while performing the procedures using general anesthesia and a high-rate, low-volume ventilation protocol. The following diagram constitutes a general overview of the protocol:

2.2 Study objectives

2.2.1 Primary objective

To determine if the proposed *ablation-by-LAW* protocol is non-inferior in terms of long-term clinical outcomes when compared to other AF ablation protocols using higher AI targets, not adapted to the LAWT.

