3. METHODS

3.1 Study design

Single-arm, international, multicenter, prospective study.

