3.5 Outcomes

3.5.1 Primary endpoint

The primary endpoint will be survival free of any atrial arrhythmia at 1-year follow-up. From this endpoint, important definitions must be taken into account:

- AF recurrence will be considered only after the 3-month ‘blinking period’ (see below), whenever the patient refers clear symptoms of recurrence (fast, recurrent palpitations with abrupt onset and termination, lasting for several minutes or hours), if AF is documented in an electrocardiogram (ECG), or whether it is recorded in a Holter registry (> 30 seconds).
- The ‘blinking period’ refers to the first 3-month period after the PVI procedure, where a transient increased risk of post-procedural atrial tachyarrhythmias is expected to occur due to pro-arrhythmogenic inflammatory changes after creating tissue RF lesions.

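### The primary objective and hypothesis claim more than a single-arm, 1-year study with CLOSE as its only named comparator can support, and the analysis section fixes no benchmark, margin or decision rule

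*Combined protocol and SAP*

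**What the plan says.** The efficacy claim is worded against three different comparators.

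- Section 2.1 (hypothesis): the approach is "at least as effective as the current AF ablation standards". No standard is named.
- Section 2.2.1 (primary objective): it is to be "non-inferior in terms of long-term clinical outcomes when compared to other AF ablation protocols using higher AI targets", those protocols being ones not adapted to wall thickness. This is a class with no named member.
- Section 3.11.1 (sample size): the assumption is that it "is an acceptable alternative to the CLOSE protocol". This is one protocol.

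The design is given in 3.1 as "Single-arm, international, multicenter, prospective study". The primary endpoint in 3.5.1 is "survival free of any atrial arrhythmia at 1-year follow-up", and 3.7 and 3.8 schedule no visit after 12 months. The introduction reports CLOSE "with 91.3% of the patients free from AF/AT/atrial flutter (AFL) at 12 months follow-up"; 3.11.1 does not repeat that rate. The introduction also cites another series: "The same 550 and 400 AI target values were used in a retrospective study comparing AI vs. CF-guided ablation", without giving its success rate. Section 3.11.1 states a 10% margin and then a limit of -0.05 for a one-sided 95% interval. For the primary endpoint, 3.11.2 names Kaplan-Meier analysis and nothing else.

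**The concern.** In a randomised trial the control arm supplies the comparison, and loose wording in the objective does limited damage. Here there is no control arm. The external rate minus the margin is the decision threshold, so the choice of comparator and margin is part of the test.

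Two things are at stake. The first is the reach of the conclusion: success against one published 12-month result would let the study report its primary objective as met for a class of protocols, and over a long-term horizon, on which it has no data. The second is the threshold. The class has at least two members by the introduction's own account, and the analysis section ties the result to neither of them. As worded, the objective could be declared met against whichever higher-target series had the lowest reported success.

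**Working it through.** **Scope, set side by side**

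| Element | Claimed (2.1, 2.2.1) | Available in the design |
|---|---|---|
| Comparator | current standards; a class of higher-target protocols | CLOSE, named in 3.11.1 only |
| Horizon | long-term | 1 year (3.5.1); last visit at 12 months |
| Outcome | clinical outcomes, plural | arrhythmia-free survival |
| Decision rule | non-inferior | none in 3.11.2; a confidence-limit criterion in 3.11.1 only |

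CLOSE used Ablation Index targets fixed by wall (400 posterior, 550 anterior). The trial uses 300 to 500 according to thickness (3.4.3). CLOSE is therefore a protocol not adapted to thickness, and it falls within the class in the objective.

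**The plan's own figure**

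Section 3.11.1 gives n = 106 for 90% power with 10% drop-out included, but no assumed success rate. Taking 91.3% as both benchmark R and true rate, a 10-point margin and one-sided 5%:

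n = [1.645 × √(0.813 × 0.187) + 1.282 × √(0.913 × 0.087)]² / 0.10² = 101 after rounding up; 101 / 0.9 rounds up to 113.

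This does not reproduce 106. At 5 points the same formula gives 344, or 383 with drop-out. That is a separate matter and does not affect the comparator question.

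**Pass mark against CLOSE**

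Inputs: R = 0.913 (introduction), treated as a known constant; margin d = 0.10 or 0.05 (both in 3.11.1); evaluable patients 106 × 0.9 = 95.4, taken as 95; exact (Clopper-Pearson) one-sided 95% lower limit L(x) for x successes. The pass mark is the smallest x with L(x) > R - d.

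- d = 0.10, floor 0.813: L(83) = 0.803 fails and L(84) = 0.816 passes. Pass mark 84/95 (88.4%).
- d = 0.05, floor 0.863: L(87) = 0.853 fails and L(88) = 0.866 passes. Pass mark 88/95 (92.6%).

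If all 106 are evaluable, the pass marks are 94/106 (88.7%) and 98/106 (92.5%). At a true rate of 91.3% and 95 evaluable, the chance of passing is 87.8% at 10 points and 40.9% at 5 points. The unresolved margin alone therefore moves the threshold by four patients, with CLOSE as the only comparator.

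**How far the threshold would move with another comparator**

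The documents give no 12-month success rate other than 91.3%. The other rates below are assumptions for illustration. All use a 10-point margin and 95 evaluable.

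| Comparator rate | Floor | Pass mark | Chance of passing if true success is 81.3% |
|---|---|---|---|
| 91.3% (CLOSE) | 81.3% | 84 (88.4%) | 4.4% |
| 88% (assumed) | 78% | 82 (86.3%) | 12.9% |
| 85% (assumed) | 75% | 79 (83.2%) | 37.9% |
| 80% (assumed) | 70% | 75 (78.9%) | 76.8% |

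At a 5-point margin the pass marks are 88 (CLOSE), 83 (assumed 85%) and 79 (assumed 80%). Against an assumed 85% the last column then falls from 37.9% to 7.8%.

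**The case against.** The strongest reply is that a general objective made specific in the statistical section is ordinary protocol structure. Section 3.11.1 names CLOSE and applies the margin to the difference between the two protocols, the only 12-month success rate in the documents is CLOSE's, and 3.5.1 states 1 year openly. No section proposes a different comparator. Much of this stands, and it rules out three stronger readings that a reader might infer.

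- **That the primary objective goes untested.** It does not, because CLOSE is a member of the class. The objective is addressed for one member at one time point.
- **That a formal test against CLOSE is planned and merely mislabelled.** This credits the plan with too much. CLOSE and the confidence-limit criterion appear only in the sample-size reasoning; 3.11.2 carries neither.
- **That 38% and 77% are false-positive rates.** They are not. A true rate of 81.3% is 3.7 points below an 85% comparator and above an 80% one, so it is non-inferior to both at 10 points, and passing would be the correct result. These figures become error rates only with respect to CLOSE, and only if CLOSE were replaced after the data were seen. Nothing in the documents plans that.

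The reply does not remove the gap between the wording of 2.1 and 2.2.1 and the design, or the absence of a rule in 3.11.2 that would hold the conclusion to CLOSE.

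**Conclusion.** The concern holds as a mismatch of scope joined to a missing decision rule. The most that this design can support is a statement about 1-year arrhythmia-free survival relative to the published CLOSE result. Statements about other higher-target protocols, current standards or durability beyond 12 months would have no support from the study's data.

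For CLOSE alone, the threshold is 84/95 or 88/95 depending on which figure in 3.11.1 is the margin. This rests on 95 evaluable patients, an exact binomial limit, complete 1-year status in those patients, and 91.3% taken without sampling error; the documents do not give the number of patients behind it. A limit from Kaplan-Meier with censoring would differ somewhat. The pass marks of 82, 79 and 75 rest on assumed comparator rates and show only how sensitive the threshold is. The change should be made before analysis, but it is a matter of wording and specification that the existing design can absorb.

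**What to change.** 1. Restate 2.1 and 2.2.1 with one claim: 1-year arrhythmia-free survival with ablation-by-LAW is non-inferior to that reported for CLOSE. Remove the references to long-term outcomes, to other protocols as a class and to current standards.
2. State that CLOSE is the only confirmatory comparator. Comparisons with any other published protocol are descriptive and cannot support a non-inferiority claim.
3. Put the decision rule in 3.11.2: the benchmark fixed at 91.3%, with its source; one margin, after reconciling the 10% and -0.05 in 3.11.1; and the requirement that the lower one-sided 95% limit of the 1-year estimate exceed benchmark minus margin. Name the interval method.

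Rewording 2.1 and 2.2.1 alone would not be enough, because the pass mark would stay open between 84 and 88 of 95.

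The cost is a protocol amendment to three sections and the reconciliation in 3.11.1. No extra visits or data items are needed. If the smaller margin is the intended one, the sample size would have to be revisited, as the power figures above show. The downside is a narrower claim.
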